10. CONCOMITANT MEDICATIONS AND NON-DRUG THERAPIES

Subjects will be instructed to inform the investigator prior to starting any new medications from the time of first dose of study treatment until the end of the study (Final Study Visit). Any concomitant medication(s), including non-prescription medication(s) and herbal product(s), taken during the study will be recorded in the electronic case report form (eCRF). Additionally, a complete list of all prior anti-cancer therapies will be recorded in the eCRF.

If future changes are made to the list of permitted/prohibited medications, formal documentation will be provided by the Coordinating Center and stored in the study file. Any such changes will be communicated to the investigative sites in the form of a letter.

As trametinib is metabolized predominantly via deacetylation likely mediated by hydrolytic esterases, its PK is unlikely to be affected by other agents through metabolic interactions. Trametinib repeat-dose exposure was not affected by co-administration with a CYP3A4 inducer.

Based on *in vitro* and *in vivo* data, trametinib is unlikely to significantly affect the PK of other medicinal products via interactions with CYP enzymes or transporters.

Any questions regarding concomitant medications should be directed to the Medical Monitor for clarification.

10.1. Permitted Medication(s)

Subjects should receive full supportive care during the study, including transfusion of blood and blood products, and treatment with antibiotics, antiemetics, antidiarrheals, and analgesics, and hematopoietic growth factors as appropriate.

10.2. Prohibited Medications and Non-Drug Therapies

The use of certain medications prior to the first dose of study treatment (refer to inclusion and exclusion criteria, Section 5.2) and for the duration of the study will not be allowed. If a prohibited medication is required for single use (such as for a procedure) while treatment with study treatment is interrupted, the Medical Monitor can approve such use.

The following medications or non-drug therapies are prohibited:

- Anticancer agents: Additional investigational or commercial anticancer agents such as chemotherapy, immunotherapy, targeted therapy, biological response modifiers, or endocrine therapy will be prohibited.
- Herbal therapies: Subjects will abstain from using herbal preparations/medications within 14 days prior to the first dose of Trametinib and throughout the study until the end of treatment visit. These herbal medications include, but are not limited to, St. John's wort, kava, ephedra (ma huang), ginkgo biloba, dehydroepiandrosterone (DHEA), yohimbe, saw palmetto, and ginseng.

CONFIDENTIAL

The investigator should contact the Medical Monitor before initiating treatment with any herbal preparation.

11. LIFESTYLE AND/OR DIETARY RESTRICTIONS

11.1. Contraception

11.1.1. Female Subjects

A female of non-childbearing potential (i.e., physiologically incapable of becoming pregnant) is defined as any female who has had a hysterectomy, bilateral oophorectomy (ovariectomy) or bilateral tubal ligation, or is post-menopausal.

A practical definition accepts menopause after 1 year without menses with an appropriate clinical profile, e.g., age appropriate, >45 years in the absence of hormone replacement therapy (HRT). In questionable cases, the subject must have a follicular stimulating hormone (FSH) value >40 mIU/mL and an estradiol value < 40pg/mL (<140 pmol/L).

A female of childbearing potential is defined as any female who does not meet the criteria of non-childbearing potential as described in the previous paragraph.

Female subjects of childbearing potential must not become pregnant during the study and so must be sexually inactive by abstinence or use contraceptive methods with a failure rate of <1%.

Abstinence

Sexual inactivity by abstinence must be consistent with the preferred and usual lifestyle of the subject. Periodic abstinence (e.g., calendar, ovulation, symptothermal, post-ovulation methods) and withdrawal are not acceptable methods of contraception.

Complete abstinence from sexual intercourse for 14 days prior to first dose of study treatment, through the dosing period, and for at least four months after the last dose of study treatment.

Contraceptive Methods with a Failure Rate of <1%

- Oral contraceptives (either combined or progesterone only) if not contraindicated for this subject population or per local practice.
- Estrogenic vaginal ring if not contraindicated for this subject population or per local practice.
- Percutaneous contraceptive patches if not contraindicated for this subject population or per local practice.
- Implants of levonorgestrel if not contraindicated for this subject population or per local practice.
- Injectable progesterone if not contraindicated for this subject population or per local practice.

CONFIDENTIAL

- Intrauterine device or intrauterine system that meets the <1% failure rate as stated in the product label
- Male partner sterilization (vasectomy with documentation of azoospermia) prior to the female subject's entry into the study, and this male is the sole partner for that subject. For this definition, "documented" refers to the outcome of the investigator's/designee's medical examination of the subject or review of the subject's medical history for study eligibility, as obtained via a verbal interview with the subject or from the subject's medical records.
- Double-barrier method: condom and occlusive cap (diaphragm or cervical/vault caps) plus vaginal spermicidal agent (foam/gel/film/cream/suppository)

These allowed methods of contraception are only effective when used consistently, correctly and in accordance with the product label. The investigator is responsible for ensuring subjects understand how to properly use these methods of contraception.

11.1.2. Male Subjects

To prevent pregnancy in a female partner, male subjects must use one of the following contraceptive methods from the beginning of the study until 90 days after the last dose of study treatment:

- Abstinence, defined as sexual inactivity consistent with the preferred and usual lifestyle of the subject. Periodic abstinence (e.g. calendar, ovulation, symptothermal, post-ovulation methods) and withdrawal are not acceptable methods of contraception.
- Condom (*during non-vaginal intercourse with any partner - male or female*) **OR**
- Double-barrier method: condom and occlusive cap (diaphragm or cervical/vault caps) plus spermicidal agent (foam/gel/film/cream/suppository) (*during sexual intercourse with a female*)

11.2. Lactation Restrictions

Female subjects who are lactating must discontinue nursing prior to the first dose of study treatment and must refrain from nursing throughout the treatment period and for four months following the last dose of study treatment.

12. DATA MANAGEMENT

Each participating institution will be collaborating with Vanderbilt on patient accrual. Data will be collected using a centralized electronic case report form called ON-line Clinical Oncology Research Environment = Oncore

[REDACTED] Oncore is a highly secure, web based, cancer specific, and customizable system that provides fully integrative clinical data management and study administration capabilities developed in an ongoing collaborative effort with NCI designated Comprehensive Cancer Centers. It fully integrates study administration functionality including protocol tracking, patient registration, NCI reporting, review committee tracking, and SAE tracking, with clinical data management

CONFIDENTIAL

functionality including electronic case report forms (eCRF) design, clinical data capture, protocol and regulatory compliance monitoring. Also the system is capable in storing basic protocol information (e.g., IRB approval dates, dates for annual renewals, etc.) and clinical trials research data. Oncore allows the investigator to define specific protocol requirements and generate data collection forms. Creation of the data collection form is done with a single button click after the parameters of an individual protocol have been specified. Oncore permits specification of study protocols, management of patient enrollment, clinical data entry and viewing, and the generation of patient or study-specific reports based on time stamping. OnCore is embedded with a comprehensive domain repository of standard reference codes and forms to promote standardization. The sources for the repository include CDUS, CTC, CDEs from NCI, ICD, MedDRA and various best practices from contributing NCI-designated Comprehensive Cancer Centers. OnCore provides several reporting features specifically addressing NCI Summary 3 and Summary 4 and other reporting requirements. Data may also be exported in a format suitable for import into other database, spreadsheets or analysis systems (such as SPSS). This system will be used to manage all VICC clinical trials data. OnCore is maintained and supported in the VICC Clinical and Research Informatics Resource.

Specified members at each participating site will submit all pertinent regulatory documents to the Coordinating Center team member, who will upload it on Oncore.

The Principal Investigator or designee will inform the sponsor within 24 hrs of any serious adverse event, and will inform the IRB in accordance with each institution's IRB policy. The investigator is responsible for the detection and documentation of events meeting the criteria and definition of an AE or SAE, as provided in this protocol. During the study when there is a safety evaluation, the investigator or site staff will be responsible for detecting, documenting, and report AEs and SAEs, as detailed in the protocol. Furthermore, the investigator will be required to provide periodic (monthly) safety updates on the conduct of the study at his/her site and notification of study closure to the SRC/IRB. If any problem is identified related to the conduct of this research, the VICC Data Safety and Monitoring Committee (DSMC) will be formally asked to review the study and the situation that required DSMC intervention.

13. DATA ANALYSIS AND STATISTICAL CONSIDERATIONS

13.1. Hypothesis

The primary objective is to determine whether trametinib is an effective targeted therapy in BRAF nonV600^{MUT} melanoma. The hypothesis described below will apply to cohort A ("high activity" mutations and fusion events). The null hypothesis is that the objective response rate (ORR; percentage of patients achieving a confirmed CR or PR is not attractive (defined as $\leq 5\%$). The alternative hypothesis is that the response rate is of interest for further development (defined as $\geq 25\%$).

The final analysis of the overall response rate will be performed using one sided test with $\alpha=0.05$. It is calculated that at least 4 responses are needed out of a total of 25 patients to reject the null hypothesis.

To allow early termination of the trial due to lack of efficacy, the trial will be conducted in two stages per Simon's Minimax Design. If no responses are demonstrated in the first 15 patients, then the trial will be terminated early for futility. If ≥ 1 responses are observed,

CONFIDENTIAL

enrollment will continue to 25 patients.

For the experimental arm (cohort B), the trial will also be conducted in two stages. If no responses are demonstrated in the first 15 patients, then the cohort will be terminated early for futility. If ≥ 1 responses are observed, enrollment will continue to a maximum of 25 patients. Additionally, when cohort A accrual has completed, cohort B will close and not accrue further patients.

Given the rapid changes in melanoma therapies, we will also have the option of closing either cohort if the clinical activity is low. If one or two responses occur in cohort A from the first 15 patients, the principal investigators and Coordinating Center will have the option of closing the trial at the interim analysis. The principal investigators must be in universal agreement for this to occur.

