5. STUDY POPULATION

5.1. Number of Subjects

The number of subjects enrolled will be dependent on the early response rate. In stage I, 15 subjects will be enrolled in cohort A and if less than one response is confirmed, the trial will be terminated. If one or more responses are observed, an additional 10 subjects will be enrolled. For cohort B, we will enroll patients concurrently. In stage I we will enroll up to 15 patients. If no responses are seen, this arm will be terminated. If one or more responses occur, we will accrue up to 10 additional patients. However, this exploratory study arm will close at the completion of cohort A accrual.

CONFIDENTIAL

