13.2. Sample Size Assumptions

To determine the overall sample size and the interim sample size, a two stage Simon's Minimax design was evaluated. To test the hypotheses (ORR=5% vs. 25%), 1 response from the first 15 subjects would be required to progress to stage 2 and a total of 25 subjects will be needed to achieve the desired type I (<5%) and type II error rate (Power>90%). The risk of incorrectly stopping the trial after stage I if the drug is effective is <1.5%.

CONFIDENTIAL

Table 20: Sample size calculations

If the True Response Rate to trametinib is: (%)	Probability of Early Termination after Stage I	Probability of Rejecting the Null Hypothesis
5%	0.463	0.034 (type I error)
10%	0.206	0.234
15%	0.087	0.525
20%	0.035	0.762
25%	0.013	0.901
30%	0.005	0.965

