13.3.1. Interim Analysis

An interim analysis will be performed for each cohort after 15 subjects have completed their first post-dose disease assessment at 8 weeks. The primary analysis of this includes a boundary for early decision on futility.

By the Simon Optimal design, it is calculated that at least 1 response of 15 subjects are needed to further progress enrolment. There is no early stopping boundary for efficacy, however if ≥ 4 patients experience CR or PR, then further planning of additional development may occur.

Core members of the Novartis clinical team will be notified of the results of the interim analysis. Investigators will be informed as to whether or not the study will be stopped prematurely.

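### The stated power (>90%) and false-stop risk (<1.5%) ignore the Section 13.1 option to close Cohort A at 1 or 2 responses of 15; at a true ORR of 25% its use could lower power to 75.1% and raise false stopping to 23.6%

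*Combined protocol and SAP*

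**What the plan says.** Section 13.1 tests an objective response rate of 5% or less against 25% or more in Cohort A, one-sided at 0.05. The cohort stops at 0 of 15 and otherwise goes on to 25, where "at least 4 responses are needed out of a total of 25 patients to reject the null hypothesis".

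The last paragraph of the same section adds a discretionary stop. Its stated reason is "Given the rapid changes in melanoma therapies, we will also have the option of closing either cohort if the clinical activity is low". The trigger is: "If one or two responses occur in cohort A from the first 15 patients, the principal investigators and Coordinating Center will have the option" to close the trial at the interim analysis. The only condition is "The principal investigators must be in universal agreement for this to occur".

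Section 13.2 justifies 25 patients as the number needed "to achieve the desired type I (<5%) and type II error rate (Power>90" per cent), and adds: "The risk of incorrectly stopping the trial after stage I if the drug is effective is <1.5" per cent. At a true rate of 25%, Table 20 gives 0.013 for early termination and 0.901 for rejecting the null.

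Neither Section 13.2 nor Table 20 mentions the option. Section 5.1 says "If one or more responses are observed, an additional 10 subjects will be enrolled", and Section 13.3.1 says "it is calculated that at least 1 response of 15 subjects are needed to further progress enrolment". Both read as though one response settles the matter.

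**The concern.** The option is a second futility region. It is written in advance, tied to the primary-endpoint count and applied at the planned interim, so it changes the probability of stopping and of rejecting the null. The quoted operating characteristics leave it out.

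Those figures are the argument for n = 25. A reader who takes them at face value would believe that an active drug has about a 1% chance of being dropped at the interim. Under Section 13.1 that chance depends on how often the investigators use an option with no numerical criterion beyond the count. The consequence is a possible loss of power and a higher chance of abandoning an effective treatment; a false claim of activity does not become more likely.

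**Working it through.** **Inputs.** Section 13.1: null 5%, alternative 25%, stop at 0/15, option at 1 or 2 of 15, reject at 4 or more of 25. Section 13.2 and Table 20: the stated operating characteristics. Let X be the number of responses in the first 15, so X ~ Bin(15, p), and let u be the probability that the option is used when X is 1 or 2. The documents give no value for u, so the full range 0 to 1 is shown.

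**Formulas.**

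- Early termination = P(X=0) + u·[P(X=1) + P(X=2)]
- Power = Σ P(X=x)·P(Bin(10,p) ≥ 4−x) over x ≥ 1, with the terms for x = 1 and x = 2 multiplied by (1−u)

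**Step 1: reproduce Table 20 (u = 0).** Early termination and rejection probability:

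| True ORR | Early termination | Reject H0 |
|---|---|---|
| 5% | 0.4633 | 0.0336 |
| 10% | 0.2059 | 0.2338 |
| 15% | 0.0874 | 0.5245 |
| 20% | 0.0352 | 0.7618 |
| 25% | 0.0134 | 0.9008 |
| 30% | 0.0047 | 0.9651 |

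These agree with Table 20 to rounding. The table is therefore correct, but for stopping at 0/15 alone.

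**Step 2: how often the option opens at 25%.** P(X=1) = 0.0668 and P(X=2) = 0.1559, which sum to 0.2227.

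**Step 3: what each closure costs in power at 25%.**

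- After 1/15, three or more of the next 10 are needed: P(Bin(10, 0.25) ≥ 3) = 0.474. Loss = 0.0668 × 0.474 = 0.0317.
- After 2/15, two or more are needed: P(Bin(10, 0.25) ≥ 2) = 0.756. Loss = 0.1559 × 0.756 = 0.1179.
- Total loss if always used = 0.1496.

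**Step 4: results at 25%.**

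| Use of the option | Early termination | Power |
|---|---|---|
| Never | 0.0134 | 0.9008 |
| 10% of the time at 1 or 2 | 0.0356 | 0.8858 |
| Always at 1, never at 2 | 0.0802 | 0.8691 |
| Half the time at 1 or 2 | 0.1247 | 0.8260 |
| Always at 1 or 2 | 0.2361 | 0.7512 |

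**Step 5: when the stated claims fail.** Power = 0.9008 − 0.1496u reaches 0.90 at u = 0.0053. Early termination = 0.0134 + 0.2227u reaches 0.015 at u = 0.0073.

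**Step 6: type I error at 5%.** 0.0336 if never used, 0.0294 if used only at 1/15, 0.0178 if always used.

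**Step 7: conditional power at the interim.** After 2/15 it is 75.6% if the true rate is 25% and 39.3% if it equals the observed 13.3%. After 1/15 the figures are 47.4%, and 2.5% at the observed 6.7%.

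**The case against.** The best defence is that Section 13.2 describes the binding Simon rule, for which its figures are right. Leaving a discretionary futility stop out of the calculation is a common convention and is conservative for type I error. The option is also in plain view in the paragraph before Section 13.2. That stands as far as it goes: nothing is miscalculated and nothing is hidden. It does not rescue the two claims, which carry no qualification, and the numerical effect of the option appears nowhere.

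Second, closing every time at 1 or 2 of 15 would require unanimity on every occasion, so 75.1% and 23.6% are extremes. Agreed. But closing at 1/15 alone gives 86.9% and 8.0%, and using the option one time in ten gives 88.6% and 3.6%. The very low thresholds in Step 5 mainly reflect how close 90.08% is to 90%.

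Third, Section 14.6 already lets the Coordinating Center terminate the study at any time. That clause is not tied to the response count, so its effect cannot be computed; the effect of this one can.

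Fourth, the calculation treats all 15 stage I outcomes as known. The interim follows the first 8-week assessment (Section 13.3.1), whereas confirmation takes at least four more weeks (Section 7.5), so the count acted on could differ from the final confirmed count. This is a fair caveat, and it applies equally to Table 20.

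Finally, stopping at 1 or 2 of 15 may be a sensible judgement, particularly at 1/15. The point here does not depend on its being a bad one.

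**Conclusion.** The concern holds. Power above 90% and false-stop risk below 1.5% are correct for the 0/15 rule and hold for the design in Section 13.1 only if the option is practically never used. At a true rate of 25%, the plan as written supports a range rather than a single figure: power 90.1% down to 75.1%, false-stop risk 1.3% up to 23.6%. Where the trial falls in that range cannot be determined from the documents.

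This rests on exact binomial outcomes, stage I responses known at the interim, and closure under the option counting as failure to reject the null. The final test is unaffected and type I error stays at or below 3.4%. The design remains valid; its stated operating characteristics omit a stopping rule that the protocol itself contains, and this should be corrected.

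**What to change.** Keep n = 25, the 0/15 rule and the final threshold of 4 responses.

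- **Section 13.2:** say that the power and false-stop figures apply when the option is not used, and give the range at 25%.
- **Table 20:** add two columns for the option always used, labelled as the outer bound:

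| True ORR | Early termination | Reject H0 |
|---|---|---|
| 5% | 0.964 | 0.018 |
| 10% | 0.816 | 0.139 |
| 15% | 0.604 | 0.353 |
| 20% | 0.398 | 0.575 |
| 25% | 0.236 | 0.751 |
| 30% | 0.127 | 0.868 |

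- **Section 13.1:** state that closure under the option means the null is not rejected. With at most 2 responses the threshold of 4 cannot have been met, but the text does not say how a cohort closed at 15 is reported. Reconcile the option with the earlier sentence in the same section that sends any cohort with a response on to 25.
- **Sections 5.1 and 13.3.1:** cross-refer to the option.

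The cost is a few sentences and two columns, with no extra patients; the drawback is a less favourable stated power. Removing the option is an alternative for the sponsor to weigh, not a required change.

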13.2. Sample Size Assumptions

To determine the overall sample size and the interim sample size, a two stage Simon's Minimax design was evaluated. To test the hypotheses (ORR=5% vs. 25%), 1 response from the first 15 subjects would be required to progress to stage 2 and a total of 25 subjects will be needed to achieve the desired type I (<5%) and type II error rate (Power>90%). The risk of incorrectly stopping the trial after stage I if the drug is effective is <1.5%.

CONFIDENTIAL

Table 20: Sample size calculations

If the True Response Rate to trametinib is: (%)	Probability of Early Termination after Stage I	Probability of Rejecting the Null Hypothesis
5%	0.463	0.034 (type I error)
10%	0.206	0.234
15%	0.087	0.525
20%	0.035	0.762
25%	0.013	0.901
30%	0.005	0.965

13.3. Data Analysis Considerations

Data will be listed and summarized according to Novartis integrated data standards library (IDSL) reporting standards where applicable. Complete details will be provided in the Reporting and Analysis Plan (RAP). Analyses will be performed for each cohort.

13.3.1. Interim Analysis

An interim analysis will be performed for each cohort after 15 subjects have completed their first post-dose disease assessment at 8 weeks. The primary analysis of this includes a boundary for early decision on futility.

By the Simon Optimal design, it is calculated that at least 1 response of 15 subjects are needed to further progress enrolment. There is no early stopping boundary for efficacy, however if ≥ 4 patients experience CR or PR, then further planning of additional development may occur.

Core members of the Novartis clinical team will be notified of the results of the interim analysis. Investigators will be informed as to whether or not the study will be stopped prematurely.

